#### [name]

- 4. Photographs may be taken of the subject's mouth for publication and/or research development purposes, no diagnosis, treatment or decisions will be made from the photographs.
- 5. A salivary flow test will be performed to determine if there is any hyposalivation.
- 6. Subjects will be asked to complete a Visual Analog Scale (VAS) for mouth dryness for a baseline mouth dryness score prior to dosing.
- 7. Sealed envelope is opened, and treatment order noted.
- 8. Subjects will not be allowed to eat or drink during the study visit except for when directed by study staff.
- 9. Subjects will self-administer 1-2 sprays into their mouth using the first sample assigned based on the randomization card.
- 10. Subjects will be asked to answer 1 question regarding mouth dryness at 5-, 15-, 30-, 60-, 120-, and 240-minutes post single dose, using a Visual Analog Scale (VAS) assessment format and a PPAQ format of none/no relief, not enough, some/good, very good, significant/excellent.
- 11. Also, subjects will be asked to answer an additional PPAQ on the secondary endpoints at 5-, 15-, 30-, 60-, 120-, and 240-minutes post single dose using a format- poor, fair, good, very good, excellent.
- 12. The subjects will be given a subject diary and instructed to record frequency of use, number of sprays, and any side effects and/or adverse events they experience while using their assigned study product.
- 13. Subjects will be instructed to use the product at home for 7 days. They will be scheduled to return to the clinic with their product container and subject diary. They will present for their follow-up appointment without having taken any of their sample product.
- 14. Subject will be instructed on restrictions during the study regarding food, medicine, oral care products, gum, hard candy.
- 15. Subjects will be instructed to use the product at home at least 1X/day.
- 16. Subjects will be instructed to call the clinic if they experience any adverse events.

Page 20 of 36 Status: Release

Version: 3

Issue Date: 07/11/2019 03:08:44 PM CDT

#### [name]

17. Subject will be scheduled for a 1-hour appointment on the 7th day of Baseline Period 1 treatment.

#### Visit 4 - End of Treatment Period 1

- 1. Subjects will not be allowed to eat or drink during their study visit except when directed by study staff.
- 2. Confirm there were no changes to medications.
- 3. Photographs may be taken of the subject's mouth for publication and/or research development purposes. No diagnosis, treatment, or decisions will be made from the photographs.
- 4. A study examiner will perform an oral exam and perform an assessment using the Challacombe-Scale to determine the severity level of dry mouth.
- 5. Subject will be asked to complete questionnaire on product efficacy, usability and acceptability.
- 6. Subjects will return the sample bottle, to the research staff who will record its weight. They will also return their completed diary to the clinic research staff.
- 7. Subjects will be instructed on restrictions during the study regarding food, medicine, oral care products, gum, hard candy.
- 8. Subjects will be instructed about the wash-out period and told to use only the oral care products supplied by the study staff for at least a 2-day wash-out period. Additional study-supplied oral products may be distributed if needed.
- 9. Subjects will be scheduled to return in a minimum of 2-days for the period 2 treatment.

#### Visit 5-Baseline Period 2

- 1. Confirm subject completed the 2-day wash-out period.
- 2. Confirm there were no changes in medications.
- 3. Subjects will not be allowed to eat or drink during the scheduled study visit except when directed by study staff.

Page 21 of 36 Status: Release

Version: 3

Issue Date: 07/11/2019 03:08:44 PM CDT

#### [name]

- 4. Photographs may be taken of the subject's mouth for publication and/or research development purposes. No diagnosis, treatment or decisions will be made from the photographs.
- 5. Subjects will be asked to complete a Dry Mouth Inventory (DMI) questionnaire to document their opinion on their severity of dry mouth prior to any dosing.
- 6. Subjects will be asked to complete a Visual Analog Scale (VAS) for mouth dryness for a baseline mouth dryness score prior to any dosing.
- 7. A study examiner will perform an oral exam and perform an assessment using the Challacombe-Scale to determine the severity level of dry mouth prior to any dosing.
- 8. Subjects will be placed into their Period 2 treatment group.
- 9. Subjects will self-administer a 1 to 2 spray dose into their mouth of their assigned sample product.
- 10. Subjects will be asked to answer 1 question regarding mouth dryness at 5-, 15-, 30-, 60-, 120-, and 240-minutes post single dose, using a Visual Analog Scale (VAS) assessment format and a Product Performance Attribute Question (PPAQ) format of none/no relief, not enough, some/good, very good, significant/excellent.
- 11. Also, subjects will be asked to answer an additional PPAQ on the secondary endpoints at 5-, 15-, 30-, 60-, 120-, and 240-minutes post single dose using a format- poor, fair, good, very good, excellent.
- 12. The subjects will be given a subject diary to record frequency of use, number of sprays, and any side effects and/or adverse events.
- 13. Subjects will be instructed to use the product at home for 7 days and return to the clinic with the randomized sample and subject diaries on the 7th day prior to any doses of the randomized sample have been administered.
- 14. Subject will be instructed on restrictions during the study regarding food, medicine, oral care products, gum, hard candy.
- 15. Subjects will be instructed to use the product at home at least 1X/day.

Page 22 of 36 Status: Release

Version: 3

Issue Date: 07/11/2019 03:08:44 PM CDT

#### [name]

- 16. Subjects will be instructed to call the clinic if they experience any adverse events.
- 17. Subject will be scheduled for a 1-hour follow-up appointment on the 7th day of period 2 treatment.

#### Visit 6-End of Treatment Period 2

- 1. Subjects will not be allowed to eat or drink during the study visit except for when directed by study staff.
- 2. Confirm there were no changes to medication.
- 3. Photographs may be taken of the subject's mouth for publication and/or research development purposes, no diagnosis, treatment or decisions will be made from the photographs.
- 4. A study examiner will perform an oral exam and perform an assessment using the Challacombe-Scale to determine the severity level of dry mouth.
- 5. Subjects will return the sample bottle, to the research staff who will record its weight. They will also return their completed diary to the clinic research staff.
- 6. Subject will be asked to complete various questionnaire regarding product efficacy, usability, acceptability and preference. After these questionnaires are completed the subject has completed the study.
- 7. No further follow-up will be required, unless an adverse event occurred. In the case of an AE, the subject should continue to be followed until the AE has resolved.

See Appendix A for a table that summarizes the protocol procedures that will be performed at screening and for treatment.

#### 5.2 Medication(s)/Treatment(s) Permitted

Subjects will not be permitted to take new or change the dosing of medications at the time of randomization that will change their dry mouth conditions during the study. Otherwise, there will be no medication or treatment restrictions for the duration of the study. Subjects will be expected to only use dry mouth oral care relief and oral hygiene study products provided. In general, subjects will not be permitted to use non-study products that affect, exacerbate or alleviate their dry mouth symptoms other than the study products provided.

Page 23 of 36 Status: Release

Version: 3

Issue Date: 07/11/2019 03:08:44 PM CDT

#### [name]

## 6. Assessment of Efficacy

# 6.1 Efficacy Parameters

- Primary endpoint
  - Mouth dryness
- Secondary endpoints
  - o Feels comfortable in the mouth
  - o Effectively lubricates the mouth
  - o Soothing to the mouth
  - o Effectively moistens the mouth
  - Acceptance questionnaire
    - Likeability of flavor and mouth feel
    - o Helps with eating, chewing, swallowing and speech difficulties
    - o Fights malodor
    - Helps freshen breath
    - o Improves my quality of life
  - Usability questionnaire

#### 6.2 Assessment Methods

## Oral Tissue Exam

An oral tissue exam conducted by the study examiner will be completed at all visits to assess the soft palate, hard palate, oral mucosa, attached gingiva, tongue, sublingual and submandibular areas, salivary glands, tonsillar and pharyngeal areas, and teeth. Assessment responses will be given as Normal or Abnormal.

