#### **Risk Minimization**

Efforts to minimize risks to study subjects will be made with the following approaches:

- Compliance with ISO 10993
- Selection of investigators who are experienced dental clinicians
- Clearly defined inclusion and exclusion criteria will be used to ensure only appropriate subjects are enrolled
- Ensuring that treatment and follow-up of subjects is consistent with current dental practice
- Monitoring of investigational sites and patients
- Review of reported Adverse Events

Based on the biocompatibility and a general risk review, the possible side effects of using the experimental device include:

- Potential stinging or burning sensations associated with the product
- Sloughing of the superficial soft tissues in the oral cavity such as the inside surface of the cheeks
- Paresthesia (local numbing for a short period of time)
- Soft tissue erythema and edema
- The product could accidentally be splashed into the eye and minor, limited irritation may occur
- Allergic reaction to the product

Benefits: There may be no direct benefits to the participants in this study. However, information obtained in this investigation may benefit others in the future.

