#### Challacombe Scale

The Challacombe Scale will be conducted prior to any dosing at all visits. Subjects with a score of 0 will not be enrolled in the study. Subjects with a score of 1 or greater, will be enrolled.

Page 24 of 36 Status: Release

Version: 3

Issue Date: 07/11/2019 03:08:44 PM CDT

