## 7. Assessment of Safety

## 7.1 Safety Parameters

The principal measures of safety will be the incidence of adverse events reported during the study.

Only treatment-emergent adverse event will be reported.

Examples of anticipated adverse events are:

- Temporary and mild, mouth or tongue sensations such as:
  - Numbness
  - o Burning sensation
  - o Tingling sensations
  - Taste alteration
- Superficial tissue sloughing on the inner surface of the cheeks, which is transient and painless.

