# 8.2.2 Safety Analyses

All adverse events (AEs) occurring after initiation of study treatment (treatment emergent AEs) will be summarized by severity, relatedness, overall and treatment group. AEs occurring during the screening period will be summarized separately. All AEs will be classified using the MedDRA dictionary.

All verbatim descriptions will be listed for all AEs, along with information regarding onset, duration, severity, relationship to treatment, and action taken.

Serious adverse events will be summarized and presented according to nature, time to onset, duration, relationship to treatment and outcome.

Fisher's Exact tests will be carried out to compare each preferred term between treatment groups. Testing will be carried out at a two-sided alpha level of 0.05.

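### The oral tissue exam is scored only Normal or Abnormal, is not compared with the pre-dose exam and feeds no safety table, so a new local effect counts only if someone separately reports an adverse event

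*Combined protocol and SAP*

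**What the plan says.** Section 6.2 (Oral Tissue Exam) provides that "An oral tissue exam conducted by the study examiner will be completed at all visits". The exam is "to assess the soft palate, hard palate, oral mucosa, attached gingiva, tongue, sublingual and submandibular areas", together with the salivary glands, the tonsillar and pharyngeal areas and the teeth. Its output is given in one sentence: "Assessment responses will be given as Normal or Abnormal". Appendix A schedules it at all six visits. Under Section 5.1 the Visit 3 and Visit 5 exams come before dosing, and Visits 4 and 6 close the two home-use periods. Section 3.3 blinds the evaluator to product for exams after randomization; subjects are not blinded.

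Section 1.3 lists local tissue effects among the possible side effects, including superficial sloughing and "Soft tissue erythema and edema". Section 3.2 makes clinical safety a secondary endpoint. On how safety is judged, Section 7.1 says "The principal measures of safety will be the incidence of adverse events reported during the study". Section 8.2.2 says "All adverse events (AEs) occurring after initiation of study treatment (treatment emergent AEs) will be summarized by severity, relatedness, overall and treatment group", adds AE listings and a summary of serious events, and states that Fisher's exact "tests will be carried out to compare each preferred term between treatment groups". The oral exam appears in neither section.

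**The concern.** The exam is the one scheduled, examiner-made inspection of the tissue that Section 1.3 regards as at risk. It is blinded after randomization and has a pre-dose reference in each period. Two features stop it from informing the safety conclusion. First, a two-category response with no comparison to the pre-dose exam cannot show worsening at a site that starts Abnormal, and does not say what was found at a site that becomes Abnormal. Second, no exam result goes into a planned table, and no rule says when one is to be considered as an AE.

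The first feature may matter in this population. Entry requires at least one Challacombe sign ("Subjects with a score of 1 or greater, will be enrolled"), and several of those signs concern tissues that the exam also covers.

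At stake is the local-tolerance part of the secondary safety endpoint. The comparison between sprays would depend on separately raised AE reports, partly from unblinded subjects, while the blinded observations go unused.

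**Working it through.** The plan gives no figure on this point, so the check is a reading of the sections side by side, followed by an illustration on assumed rates.

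**1. What the specified response can show.** Taking one response per site, compare the pre-dose exam (Visit 3 or 5) with the exam at the end of the same period (Visit 4 or 6):

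| Pre-dose | End of period | What the record shows |
|---|---|---|
| Normal | Normal | no finding |
| Normal | Abnormal | a new finding, type not stated |
| Abnormal | Abnormal | no change, whether the site is stable, worse or has a different finding |
| Abnormal | Normal | resolution |

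The third row is the masking. It follows from the two-category scale and needs no assumption.

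**2. What the analysis uses.** Section 7.1 uses AE incidence. Section 8.2.2 uses AE and serious AE summaries, AE listings and tests by preferred term. Neither takes in any row of the table above, including the second.

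**3. What links an exam finding to an AE.** Section 7.2 allows the investigator to identify an AE or the subject to report one, and its definition of an AE is broad. Appendix A schedules AE assessment at Visits 2 to 6. Section 7.1 names cheek sloughing as an anticipated AE; erythema and edema are not among its examples. Section 7.3 describes recording only for material-related events. The step lists for Visits 4 and 6 in Section 5.1 contain no AE assessment step; Visit 6 mentions AEs only for follow-up. So a route exists, but nothing says when an exam result enters it.

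**4. Whether sites may be Abnormal before dosing.** Challacombe signs in Section 6.2 include changes of the tongue, gingiva, palate and mucosa, all of which the exam covers. Section 1.3 expects some contact with compromised mucosa. No section says that such signs are scored Abnormal, and no rate is given.

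**5. Illustration on assumed rates.** Let i be the share of the 40 randomized subjects (Section 8.3) who develop one new local effect, and b the chance that the *affected site* was already Abnormal. Neither value is in the documents. Assume that all 40 are examined and that i and b are independent.

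- Expected Normal-to-Abnormal shifts = 40 × i × (1 − b)
- Chance of at least one shift = 1 − [1 − i(1 − b)]^40

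| b | i = 5% | i = 10% | i = 20% |
|---|---|---|---|
| 0 | 2.0; 87.1% | 4.0; 98.5% | 8.0; about 100% |
| 0.25 | 1.5; 78.3% | 3.0; 95.6% | 6.0; 99.8% |
| 0.50 | 1.0; 63.7% | 2.0; 87.1% | 4.0; 98.5% |
| 0.75 | 0.5; 39.5% | 1.0; 63.7% | 2.0; 87.1% |

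For example, i = 10% and b = 0.75 give 40 × 0.10 × 0.25 = 1.0 expected shift, and 1 − 0.975^40 = 63.7%. These are shifts present in the exam data. The number of them in a planned safety table is zero in every cell, by step 2.

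**The case against.** The strongest reply is that the trial does not depend on the exam to catch local effects. The investigator is responsible for identifying AEs, which are assessed at the same visits as the exam from Visit 2 on. The diary asks for side effects during home use. AEs are then summarized by severity and listed verbatim. A clinician who sees new cheek sloughing is looking at an event that Section 7.1 itself lists, whichever box is ticked. This stands. A reader might infer that new effects are invisible, or that safety rests on unblinded subject reports alone; the documents support neither. What remains is that the route is discretionary and not tied to the exam.

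Masking can also be overdrawn. A single Challacombe sign suffices for entry, and it could be frothy saliva or cervical caries. An abnormal tongue or gingiva hides nothing on the inner cheek, where the plan places the sloughing. Section 4.2 excludes active mouth sores. This stands too: a reader might take the share of subjects with any abnormal site as the share of effects lost, but masking requires the same site.

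The examination form mentioned in Appendix A is not in the documents, so a comment field cannot be ruled out. Free text alone would still lack a definition of worsening, a link to AE recording and an analysis.

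Finally, the exam is described under efficacy methods, the device is classed as non-significant risk, and Section 1.5 reports no AEs in two earlier studies. These facts limit the weight of the point but do not answer it.

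**Conclusion.** The point holds as a gap in recording and analysis. A blinded tissue exam that is already performed has a response that cannot show worsening at a site already Abnormal, no comparison with the pre-dose exam, no explicit link to AE recording and no planned table. New local effects count towards the safety conclusion only if the investigator or the subject separately reports an AE.

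The size of the loss is unknown. The illustration shows direction only: at an assumed 10% incidence, the chance that the exam data contain at least one shift falls from 98.5% to 63.7% as b rises from 0 to 0.75. It rests on assumed rates and says nothing about effects captured as AEs. That dry-mouth signs make a site Abnormal is a reasonable inference, not a statement in the plan. The lack of any planned use of the exam does not depend on that inference.

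The primary endpoint, its analysis and the sample size are not affected. This is a worthwhile, inexpensive improvement to the safety assessment.

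**What to change.** - **Section 6.2:** at Visits 4 and 6, record each site as unchanged, new or worsened against the pre-dose exam of the same period (Visit 3 for Period 1, Visit 5 for Period 2), with the type of finding, such as erythema, edema, sloughing or other.
- **Section 6.2 or 7.2:** state that the investigator assesses every new or worsened finding as a possible AE under the Section 7.2 definition.
- **Section 8.2.2:** add a by-product table of new or worsened findings by site and type.

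The cost is a revised form, one extra table and possibly a slightly higher AE count. The examiner and visits stay the same and no procedure is added. The examiner needs the same-period reference result but not the product assignment, so blinding can be kept.

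The change has a limit. Under Section 5.1 subjects attend Visits 4 and 6 without having used the product beforehand, and Section 7.1 describes the anticipated sloughing as short-lived. Effects that resolve before those visits would still rely on the diary and AE reports.

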#### Salivary Flow Testing

Modified Schirmer tear strip Test (MST) - Testing with unstimulated saliva flow rate taken during the baseline period 1 visit (after wash-in and water only evaluation visits) to understand if the subject has hyposalivation and further characterize the study population.

This is an objective assessment where subjects are asked not to eat, drink, chew tobacco, chew gum, smoke, brush or floss teeth for 2 hours prior to Baseline Period 1 study visit. Test strips are placed on the floor of the mouth for 3-minutes to measure unstimulated flow rates. A calibrated paper that has an indicator that shows the amount of saliva present. 

#### Challacombe Scale

The Challacombe Scale will be conducted prior to any dosing at all visits. Subjects with a score of 0 will not be enrolled in the study. Subjects with a score of 1 or greater, will be enrolled.

Page 24 of 36 Status: Release

Version: 3

Issue Date: 07/11/2019 03:08:44 PM CDT

#### [name]

This is an objective assessment to stratifying subjects into 3 groups representing their severity of dry mouth symptoms. A study examiner will conduct an oral exam and evaluate 10 symptoms. This scale works as an additive score of 1 to 10: 1 being the least and 10 being the most severe. Each symptom that is present is given a score of 1.

The Challacombe Scale of clinical oral dryness helps clinicians visually identify and quantify whether a patient has xerostomia. The 10 clinical signs are additive to determine severity.

9	Dental mirror sticks to the patient's tongue	
0	Dental mirror sticks to the buccal mucosa	Total score helps you determine
②	No saliva pooling in the floor of the patient's mouth	patient's level of dry mouth:
0	Saliva is frothy	,
0	Patient's tongue shows generalized shortened papillae	Score of 1-3 = Mild
0	Altered gingival architecture (i.e., smooth)	
0	Patient's oral mucosa, especially the palate, appears glassy	Score of 4-6 = Moderate
0	Tongue lobulated/fissured	Cana of 7 10 = Causas
0	Patient has cervical caries on more than 2 teeth	Score of 7-10 = Severe
0	Debris sticks to teeth or palate	

## Dry Mouth Inventory

http://www.challacombescale.co.uk/Challacombe-Scale-ENG.pdf

Dry Mouth Inventory (DMI) will be conducted for each sample at the Water Only Evaluation visit and the Baseline Period 2 visit prior to any dosing.

This assessment is to understand the subject's opinion on their severity of dry mouth. Subjects will be asked to respond to 4 symptoms of dry mouth:

- 1. No moisture in the mouth
- 2. Lips sticking to the teeth
- 3. Tongue sticking to the roof of mouth
- 4. Throat dryness

This is an accumulative total score on a 6-point scale: Disagree (0), Disagree a little (0), Strongly Disagree (0), Agree a little (1), Agree (2), Strongly Agree (3).

## Primary endpoint

The primary endpoint is relief of dry mouth, it will be scored using the Visual Analog Scale (VAS) - 10 cm long where the subject will score their mouth dryness. The anchor points of the scale are 0 represents "normal" (i.e., no dry mouth symptoms), and 10 representing "the worst imaginable" dry mouth symptoms.

Page 25 of 36 Status: Release

Version: 3

Issue Date: 07/11/2019 03:08:44 PM CDT

